11.0 Number of Participants

11.1 Number of Participants to be Consented:

Targeting enrollment at 264 participants in full-data collection.

For qualitative interviews, these will happen with a smaller subsample of participants enrolled. Specifically, the qualitative sample will be derived from purposive sampling of extremes^{119,120} in market adoption. Thus, participants selected for interviews will be from the highest and lowest quintiles of market shopping as measured by the number of trips to the Mobile Market during the final two months of the intervention period. The estimated number of interviews is 24 for low adopters and 24 for high adopters (48 total) selected from across intervention sites,¹²¹ however, the qualitative sample size will only be set after saturation has occurred during analysis and coding of the qualitative data.¹²¹

For our primary outcome, with our planned sample size of 264 divided between 12 clusters, we anticipate 80% power to detect a difference of 5.0 HEI points between the intervention and control groups. This calculation assumes an attrition rate of 15%, so that our final analytic sample size is 224 individuals, and a conservative ICC of 0.01. If attrition is higher or recruitment is slower, a final analytic sample of n=160 individuals will provide 80% power to detect a difference of 6.0 HEI points, which is still within the range of plausibility for the effect size of this intervention.

Furthermore, smaller effects will be detectable even with this smaller sample if the ICC is closer to the value 0.004 observed in previous studies. Additionally, for our secondary outcomes, an even smaller sample would be acceptable for analysis. For example, for the third aim, we are aiming for 24 high mobile market shopping adopters and 24 low mobile market shopping adopters (final sample size will be determined once saturation is reached).

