17.0 Statistical Considerations

17.1 Data Analysis Plan: See section 17.3

17.2 Power Analysis:

Power calculation. For the primary outcome of change in HEI scores, power is computed based on a t-test at the individual client level, but the sample size is inflated for the group randomization design by a factor of $1+(m-1)*ICC$ where m is the average cluster size and ICC is the intraclass correlation. In Co-Investigator [name]'s study with participants similar to the proposed study (i.e., from the same communities with similar income and diversity levels), the HEI SD was 11.2.⁹⁰ In our preliminary customer intercept survey study, we found an ICC of 0.0004. Therefore, to be conservative, we assume an SD of 12 and an ICC of 0.01. Under these assumptions with a two-sided type I error rate of 5%, this study will have 80% power to detect a mean difference of 5.5 HEI points between intervention and control participants with an average cluster size m of 20 and number of clusters k of 12 for a total of 264 participants (132 per group). This calculation assumes an attrition rate of 20%. Detection of a 5.0 point difference in HEI is clinically significant, as it corresponds to a lower risk of cardiovascular mortality and lower risk of all-cause mortality.¹²² Additionally, given our conservative approach, we may ultimately be adequately powered to detect even smaller differences in HEI scores between intervention and control sites.

17.3 Statistical Analysis:

Aim 1: The primary analysis will compare the mean within-person, baseline to follow-up change in HEI-2015 between the mobile market and waitlist control groups. Changes in HEI-2015 will be modeled via a Generalized Estimating Equation (GEE) linear model to account for the possible correlation of outcomes within community sites. Food insecurity, as measured by the U.S. Adult Food Security Survey Module, will be analyzed similarly. Baseline characteristics of randomized

SOCIAL PROTOCOL (HRP-580)

PROTOCOL TITLE: Mobile Food Market Cluster Randomized Trial

VERSION DATE: 1/5/2023

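### The 80% power in section 11.1 for 5.0 HEI points (and 6.0 at n=160) uses individual degrees of freedom; with 12 randomised sites it is about 74% (77%), and 11.1 and 17.2 disagree

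*Combined protocol and SAP*

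**What the plan says.** Two sections describe the power of the primary comparison.

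- **Section 11.1.** For 264 participants at 12 sites, "we anticipate 80% power to detect a difference of 5.0 HEI points between the intervention and control groups". The ICC is taken as 0.01 and 224 are expected in the analysis, because of losses to follow-up: "This calculation assumes an attrition rate of 15" percent. As a fallback, "a final analytic sample of n=160 individuals will provide 80% power to detect a difference of 6.0 HEI points". Smaller effects are said to be detectable "if the ICC is closer to the value 0.004 observed in previous studies". No SD is given.
- **Section 17.2.** "For the primary outcome of change in HEI scores, power is computed based on a t-test at the individual client level", with the sample size inflated by 1+(m−1)×ICC. In an earlier study in the same communities "the HEI SD was 11.2"; the intercept survey gave an ICC of 0.0004; and "to be conservative, we assume an SD of 12 and an ICC of 0.01". The result is "80% power to detect a mean difference of 5.5 HEI points between intervention and control participants", with m=20, k=12, 264 participants (132 per group), two-sided 5% type I error and 20% attrition. The section then calls a 5.0-point difference clinically significant.

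Section 5.1 plans 22 participants per site. Section 17.3 analyses change in HEI-2015 with a linear GEE and names neither a reference distribution nor a small-sample correction. It makes exploratory interaction analyses conditional on an effect of about the size the trial is powered to detect.

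**The concern.** There are two main faults and two smaller ones.

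1. **Degrees of freedom.** A design effect inflates the variance for clustering. It does not change the reference distribution. The treatment contrast is estimated from 12 sites, so holding the stated two-sided 5% error rate needs a t reference with roughly 12−2=10 df, not one based on about 222 individuals. With so few sites the difference is visible.
2. **Unreconciled passages.** The same 264 participants and 12 sites yield 5.0 points in one section and 5.5 in the other, with different attrition. In 17.2, m=20 and k=12 do not give 264.
3. **SD.** The outcome is a change score, but the SD is described only as an HEI SD. The plan does not say that it applies to change.
4. **Earlier ICC.** It is 0.004 in 11.1 and 0.0004 in 17.2. These may come from different sources, and neither enters the main calculation, but one may be a slip.

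At stake is whether the trial has its stated power for the difference it calls clinically significant, and which effect size the condition in 17.3 refers to.

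**Working it through.** **Inputs.** SD 12, ICC 0.01 and two-sided 5% (17.2). Analysed n: 264×0.85=224.4, taken as 224 (11.1); 264×0.80=211.2, taken as 211 (17.2); 160 (11.1). Sites: 12, and 132/22=6 per arm.

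**Formulas.** DE = 1+(n/12−1)×ICC; SE = SD×√(4×DE/n); power from the noncentral t with noncentrality difference/SE.

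For n=224: DE = 1+(18.67−1)×0.01 = 1.177; SE = 12×√(4×1.177/224) = 1.739; noncentrality for 5.0 points = 5.0/1.739 = 2.87.

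**The plan's method (n−2 df) beside the same SE with 10 df**

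| n | DE | SE | Claim | Power, n−2 df | Power, 10 df | Detectable at 80%, n−2 df | Detectable at 80%, 10 df |
|---|---|---|---|---|---|---|---|
| 224 | 1.177 | 1.739 | 5.0 | 81.6% | 73.6% | 4.89 | 5.41 |
| 211 | 1.166 | 1.784 | 5.5 | 86.6% | 79.3% | 5.02 | 5.55 |
| 160 | 1.123 | 2.011 | 6.0 | 84.3% | 76.7% | 5.67 | 6.25 |

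The 5.0-point claim therefore reproduces by the plan's method, and the other two claims are conservative by it. On 10 df, both claims in 11.1 fall below 80%, and the claim in 17.2 is nearly met.

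Two further results on 10 df: 5.0 points has 71.5% power at n=211, and 79.2% if all 264 are analysed. Reaching 80% at 5.0 points needs about 271 analysed. A simulation of site means (200,000 runs, t with 10 df) gave 73.7% for 5.0 at n=224, 79.3% for 5.5 at n=211, 76.6% for 6.0 at n=160, and type I error 4.9%.

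**Confidence interval.** Expected 95% half-width at n=224: 2.228×1.739 = 3.87 points on 10 df, against 1.971×1.739 = 3.43 on 222 df.

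**Reconciling 11.1 with 17.2.** By the plan's formula, moving from 15% to 20% attrition shifts the detectable difference from 4.89 to 5.02. A detectable difference of 5.5 corresponds to about 171 analysed, a loss of (264−171)/264 = 35%. Also 20×12=240, not 264, and 20% attrition from 22 per site leaves 17.6, not 20.

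**Sensitivity: power at 5.0 points, n=224, 10 df unless stated**

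| Change | Power |
|---|---|
| SD 11.2 | 79.2% |
| ICC 0.004 | 77.5% |
| ICC 0.0004 | 79.9% |
| SD 11.2 and ICC 0.004 | 82.8% |
| SD 11.2 and ICC 0.0004 | 85.0% |
| 8 df (assumption: two spent on wave or site type) | 71.2% |
| ICC 0.03 (assumption) | 62.4% |
| SD of change 14 (assumption) | 60.4% |

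If 12 is the SD at a single time, the SD of change is 12×√(2(1−r)). Assumed correlations of 0.4, 0.5 and 0.6 give 13.1, 12.0 and 10.7, and power of 65.8%, 73.6% and 82.5%.

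**The case against.** By the method that 17.2 declares, the claims in 11.1 are met, so the headline is a criticism of method rather than a slip in the sums. Section 17.3 specifies a GEE and names no reference distribution, so 10 df is an input that the plan does not state. An uncorrected large-sample GEE test would not lose power in this way. The plan also raised both SD and ICC above the values it had observed; with both observed values restored, power for 5.0 points exceeds 80% even on 10 df. The SD of 11.2 may already be a change-score SD, which cannot be settled from the documents. Finally, 17.3 puts confidence intervals ahead of testing.

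Part of this stands. The shortfall is moderate, it is confined to 11.1, and the SD and ICC sub-points are requests for clarification. The df argument does not fall, however. Section 17.2 claims its power at a two-sided 5% error rate, and with 12 sites that rate needs roughly site-level df; an uncorrected test would trade the lost power for excess type I error. The favourable combinations use values that the plan chose not to plan on. The emphasis on intervals does not remove the issue, because the intervals widen too.

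**Conclusion.** The concern holds. On the plan's SD of 12 and ICC of 0.01, with 6 sites per arm and 10 df, 5.0 points has about 74% power at 224 analysed, and 6.0 points about 77% at 160. The stated 80% is met at about 5.4 and 6.25 points. On those inputs, 80% for 5.0 points is not reached even without attrition. The 5.5-point claim in 17.2 is sound to within a point of power. Separately from the df question, 11.1 and 17.2 give different detectable effects and attrition rates for the same sample, and the stated formula does not reconcile them.

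The power figures rest on equal site sizes, on SD 12 applying to change in HEI, and on a site-level reference distribution. The inconsistency between the sections rests on none of these. This should be fixed; it does not undermine the design.

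**What to change.** Replace the power text in 11.1 and 17.2 with one calculation: 22×12=264, one attrition rate, the resulting m (18.7 at 15%, 17.6 at 20%) and a t reference with site-level df. Suggested text:

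*With SD 12 for change in HEI-2015, ICC 0.01, 6 sites per arm and 10 df, 224 analysed (15% attrition) give 80% power for about 5.4 points and about 74% for 5.0; 160 analysed give 80% power for about 6.25 points.*

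If 20% attrition is kept, the figures are about 5.5 points for 80% power, and 71–72% power at 5.0.

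In addition:

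- State that SD 12 is assumed for the change score, and show sensitivity to SD, ICC and df, including the df left if site type or wave enters the model.
- Give the source of each earlier ICC, or correct the wrong one.
- Name the single effect size that the interaction condition in 17.3 refers to.
- Use the same df in the GEE test and intervals in 17.3, with a small-sample correction, so that planning and analysis agree.

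The cost is protocol wording and slightly less favourable stated figures. Sample size, sites and procedures are unchanged.

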12.0 Recruitment Methods

SOCIAL PROTOCOL (HRP-580)

PROTOCOL TITLE: Mobile Food Market Cluster Randomized Trial

VERSION DATE: 1/5/2023

12.1 Community and Participant Recruitment process:

Community recruitment process:

When: After grant is awarded. Process will begin approximately 2-5 months into the grant.

Where: At/around the Twin Cities in low-income/low food access communities meeting site inclusion criteria.

Strategies: Mobile market staff will work with their ongoing community partners, sites on their waitlist (interested in service when capacity to expand is available), and new potential partners to recruit sites meeting inclusion criteria to receive mobile market service as part of the trial (depending on randomization, as either intervention or waitlist control sites). While the sites will be specifically recruited for the trial, the mobile market service at these sites will be normal mobile market service (i.e., the same service that is currently ongoing at other community site locations that are not part of the trial). At the trial site locations of this trial, anyone will be able to shop at the mobile market, not just those enrolled in the trial.

Participant recruitment process:

When: After recruitment of community sites

Where: At/around the community sites recruited for the trial before randomization of communities to mobile market service or waitlist control is known to sites, participants, research staff, the PI, and non-statistician University co-investigators.

Strategies:

- working closely with community site staff to get the information to community members
- posting flyers and tabling in central locations around recruited site locations
- attending resident meetings (e.g., resident council in public housing buildings)
- sending trial information along with community newsletters/ updates
- bringing the mobile market to each site for an informational event

Retention strategies:

- providing contact throughout the study to retain up-to-date contact information (e.g., calls/text messages/emails, reminder letters, seasonal cards, monthly newsletters),
- continuing to collect data in a convenient location
- providing culturally and linguistically competent staff

SOCIAL PROTOCOL (HRP-580)

PROTOCOL TITLE: Mobile Food Market Cluster Randomized Trial

VERSION DATE: 1/5/2023

12.2 Source of Participants: Community – specifically, community members in/around the 12 sites recruited for mobile market service as part of the trial will be recruited. See recruitment for details.

12.3 Identification of Potential Participants:

- See recruitment strategies for how potential participants will be identified (section 12.1). As additional information:
 - No recruitment will occur based on information contained in private/protected records.
 - When in-person recruitment occurs, the research staff will make initial contact by saying hello and offering to speak with potential participants when they pass by.
 - When recruitment occurs by flyer posting or newsletter, the participant will make the initial contact to reach the research staff. [Note, if information is sent via community newsletter, the information in the newsletter would be created by the research team but would be included in the normal sending of the community newsletters, such that the research staff would not have access to the community members names or addresses and the potential participant receiving the information would need to make the first contact to the research staff.]
 - Following the intervention period, a subset of participants from intervention sites who are either the highest or lowest users of the Twin Cities Mobile Market will be invited to participate in an additional interview. This will be participants who are in the highest and lowest quintile based on the number of trips made to the Mobile Market in the final two months of the intervention period. Each of these individuals will be invited during their follow-up data collection visit.

12.4 Recruitment Materials:

See attached recruitment materials:

- flyers (to be hung in common areas at community sites)
- door hangers (which can be delivered to all units within a community housing site)
- newsletter text (which could be included in a community site's newsletter or other communications with residents)
- handout (which could be distributed during tabling or other community event)
- screenshot of the study website (<http://z.umn.edu/mobilemarketstudy>; link is included on other recruitment materials)

12.5 Payment:

- Compensation (up to \$200 across measurement periods) will be offered. An additional \$20 will be provided to participants selected to participate in the qualitative interviews. More specifically:
 - Each participant will receive an incentive for specific data collection activities at baseline and follow-up data collection [\$200 total; \$100 at baseline and \$100 at follow-up]. Specifically, participants will be given \$20 for completing the psychosocial survey and first dietary recall at the in-person data collection visit, \$10 for completing the second dietary recall, and \$15 for completing the third dietary recall. Participants will be given \$10 for each week of fruit & vegetables purchase booklet collection (for weeks 1-4) and \$15 additional dollars in the final week (week 4) of fruit & vegetable purchase booklet collection, if participants collected and returned purchase receipts for the entire month. One Greenphire ClinCard pre-paid debit card will be provided at in-person measurement and the other payments will be reloaded onto the debit card after completion of the study activities (see ClinCard information form attachment for information we will collect in order to provide payments). For participants selected for qualitative interviews, qualitative interview participation will result in participants receiving an additional \$20 payment loaded to their debit card. We plan to recruit 264 and complete qualitative interviews with 48 individuals already enrolled in the study. Qualitative interviews will occur during the follow-up period of each Wave.
- No Research Experience Points will be awarded.

13.0 Withdrawal of Participants

13.1 Withdrawal Circumstances: The following are the circumstances under which participants would be withdrawn from the research without their consent:

- If they are lost to follow up
- If they behave inappropriately toward study staff
- If they show signs of diminished capacity to consent

13.2 Withdrawal Procedures: Participants will be informed that if any point they no longer wish to be in the study, they may withdraw from the study. If a participant tells the research staff they would like to withdraw from the study, the research staff will ask for and document reason for withdrawal. Any data provided by the participant will continue to be used in the study, unless they formally request that data is not used. No further data will be collected from a participant who withdraws from the study.

SOCIAL PROTOCOL (HRP-580)

PROTOCOL TITLE: Mobile Food Market Cluster Randomized Trial

VERSION DATE: 1/5/2023

13.3 Termination Procedures: This study may be temporarily suspended or prematurely terminated if there is sufficient reasonable cause (see stopping rules on the DSMP). Written notification, documenting the reason for study suspension or termination, will be provided by the suspending or terminating party to the funding agency and regulatory authorities. If the study is prematurely terminated or suspended, the PI will promptly inform the IRB and will provide the reason(s) for the termination or suspension. The study may resume once concerns about safety, protocol compliance, and/or data quality procedures are addressed and satisfy the funding agency and IRB. If the study is terminated, the study team will notify the participants of the study termination.

Data collected for the study prior to the study termination will be handled in the following manner:

- If the study is terminated due to safety reasons, the data related to AEs will be evaluated.
- If the study is terminated for any other reason, the regulatory and/or institutional document/data retention policies will apply.

14.0 Risks to Participants

14.1 Foreseeable Risks:

Data Risks and Protections: To follow participants from baseline data collection to follow-up data collection, identifiable information (e.g., names, contact information including phone, address, and other forms if available) and sensitive information (e.g., self-report of health conditions) will be collected. This collection of identifiable and/or sensitive data does pose a potential risk of a data breach. The risk of a system-wide data breach of the secure HIPAA compliant University of Minnesota Health Sciences Academic Health Center (UMNHSACH) computer/network serve is low. To minimize this potential but rare risk, all data linked to participants will be coded with a non-identifiable study ID number. Identifiable information (names, addresses, etc) will be stored on a secure password protected file on a secure UMNHSACH server and will only be accessible to those the PI has given permission. Participant forms will only contain the study ID number. De-identified data will be stored separate from identifiable information and will be accessible only to those with explicit permission of the PI and a secure password. Even with a password to the server, permission is required to access file level data. All passwords will conform to the requirements of the University of Minnesota for maximum security, which includes two factor identification.

Data collected in the field from participants will be collected primarily via REDCap surveys administered using an iPad at data collection visits. The surveys will be directly entered into the secure REDCap Database and all other windows will be closed while a participant has an iPad. If there is a technical failure with the wi-fi or iPads, paper-pen surveys will be completed. The paper-pen surveys will be entered

into the secure REDCap Database by two different study staff and verified for accuracy. Data for this study will be entered into a REDCap database, which uses a MySQL database via a secure web interface with data checks used during data entry to ensure data quality. REDCap includes a complete suite of features to support HIPAA compliance, including a full audit trail, user-based privileges, and integration with the institutional LDAP server. The MySQL database and the web server will both be housed on secure servers operated by the University of Minnesota Health Science Academic Health Center's Information Systems group (AHC-IS). The servers are in a physically secure location on campus and are backed up nightly, with the backups stored in accordance with the AHC-IS retention schedule of daily, weekly, and monthly tapes retained for 1 month, 3 months, and 6 months, respectively. Weekly backup tapes are stored offsite. The AHC-IS servers provide a stable, secure, well-maintained, and high-capacity data storage environment, and both REDCap and MySQL are widely-used, powerful, reliable, well-supported systems. Access to the study's data in REDCap will be restricted to the only specific members of the study team by username and password and permission of the PI.¹¹⁸ The REDCap database will be downloaded daily while data collection is ongoing and weekly when data collection is not actively occurring by the project manager. The REDCap data downloads will be stored on secure, password protected Box file.

Survey Risks and Protections: During the survey, residents will be asked to report on their household's own food security. It is possible that these questions could elicit an emotional response. Because we expect our study population is at high risk for food insecurity, we plan to offer all participants a handout that lists contact information for Hunger Solutions (an organization that helps people identify local food shelves and food assistance programs they may qualify for and assistance with signing up for assistance.) Assistance contacting this organization or using their website to find local food shelves will also be provided, as appropriate.

Full-Service Mobile Market Intervention Risks and Protections: The full-service mobile market intervention is a community level intervention that already exists in the Twin Cities metropolitan area (there are 24 current weekly stops). While the full-service mobile market intervention will be newly available to the community sites participating in the proposed trial, the risk of participation in the mobile grocery store is minimal and equal to participation in mobile market service not associated with the trial. For example, participants of the trial will have the same opportunity to use the mobile market as will their neighbors who may or may not be in the trial. In addition, the mobile market staff on the full-service mobile market will not know (or have access to data to know) whether customers are participants in the trial or not; thus, accidental disclosure of study participation by staff will not be possible.

14.2 Reproduction Risks: Not applicable.

14.3 Risks to Others: Not applicable.

